14.0 Withdrawal of Subjects

Participants will be discontinued from the study after informed consent and run in period, if there is insufficient text message logging(does not log at least two entries a day for 10 of 14 days) during run in period and will not be randomized in to the intervention period.

Participants will not be discontinued from the study because of non-adherence after randomization; all will remain in the study unless consent is withdrawn or there are concerns regarding patient safety. All such events will be reviewed by PI in coordination with study team.

The primary analyses will use the intent-to-treat (ITT) sample, comprised of all randomized participants. The completer sample will comprise subjects who complete the 3-month follow-up. Analyses will be carried out separately for the ITT sample and for the completer sample. Missing data for this study arising from premature exits (dropouts) will result if a patient's participation is terminated before the 3 months study period is completed.

Subjects may withdraw their consent by contacting the study team via the telephone number on the consent form.

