Exploratory Analyses: The objective of these exploratory analyses is to determine trends toward statistical significance rather than confirm/refute hypotheses with adequate statistical certainty (power). Descriptive statistics and frequency distributions will be calculated as appropriate for all demographic and baseline clinical variables for the total sample and by intervention and control groups. Data will be transformed, or semi-parametric or nonparametric analysis procedures will be used as needed. Baseline values for variables will be compared for imbalance between intervention and control group using one-way analysis of variance (or nonparametric Kruskal-Wallis one-way ANOVA) followed by a pairwise multiple comparison procedure (e.g. Tukey's procedure), if indicated.

Categorical baseline variables will be compared using chi-square analyses.

The primary analyses will use the intent-to-treat (ITT) sample, comprised of all randomized participants. The completer sample will comprise subjects who complete the 3-month follow-up. Analyses will be carried out separately for the ITT sample and for the completer sample. Missing data for this study arising from premature exits (dropouts) will result if a patient's participation is terminated before the 3 months study period is completed. Participants will not be discontinued from the study because of non-adherence; all will remain in the study unless consent is withdrawn or there are concerns regarding patient safety. We will adopt several approaches to dealing with missing data for the ITT analysis set: for continuous outcomes requiring a single endpoint end-of-study value (change from baseline to 3 months), we will use multiple imputation methods to impute missing 3-month values. We will evaluate the sensitivity of study conclusions to the presence of missing data by comparing the results of ITT to the completer analyses and the imputation results. We will use information on premature exits/missed appointments, food photography and dietary logs as indicators of participation, feasibility and fidelity of the treatment modalities being compared. Because this is a feasibility study, no adjustment will be made for analyses using the primary or secondary outcome measures.

Data Security:

Data confidentiality, Data Acquisition and Management

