If the consent is obtained via telephone, the consent form will be sent to the potential participant. Study personnel will speak with the potential participant via a telephone call to discuss the consent form and answer any questions. The participant may then sign the consent form and send the consent form to study personnel. Study personnel will sign the consent form. A signed copy of the consent form will be provided to the participant..

Example 1:

a. Our data and safety and monitoring plan will monitor all patients to ensure the safety of participants and the validity and integrity of the data. Protection to participants will be in accordance with guidelines set forth by NIH. [name] has vast experience in clinical trials and has completed several trials. The level of monitoring will be as rigorous as in the prior published clinical trials. All serious, unexpected, AND related adverse events will be reported to the IRB.

b. Study will be registered in ClinicalTrials.gov before the first subject is enrolled.

Any change in endpoints or analysis plan that occurs will be amended in ClinicalTrials.gov.

The reporting of summary results information (including adverse events) will occur no later than 1 year after the completion date.

Example 2:

All adverse events (AE) will be reported and monitored. The AE's will be characterized by: intensity/severity; expectedness; relatedness; frequency; outcome; treatment or action taken.

Monitoring will be performed at each study visit by the study coordinator and PI, adverse events will also be monitored during regularly scheduled visits (pre-intervention, weekly for first month, alternate weeks for second month and once during last month of study) with the psychologist or dietitian and such events will be reported to PI. All AEs will be recorded on an event form with physician/nurses/coordinator notes attached.

These will be reviewed by [name] and [name].

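### A patient-safety concern is grounds for leaving the study, with no separation between stopping the assigned eating pattern and leaving follow-up, so these women's primary outcome and adverse-event outcome may go uncollected

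*Combined protocol and SAP*

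**What the plan says.** Section 14.0 (Withdrawal of Subjects) sets the rule for randomized women: "Participants will not be discontinued from the study because of non-adherence after randomization", and "all will remain in the study unless consent is withdrawn or there are concerns regarding patient safety". Section 12.0 (Data Management, Exploratory Analyses) repeats it. Section 14.0 then adds one sentence on handling: "All such events will be reviewed by PI in coordination with study team".

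Both sections go on to missing data, which "will result if a patient's participation is terminated before the 3 months study period is completed". On analysis, Section 12.0 states "The primary analyses will use the intent-to-treat (ITT) sample, comprised of all randomized participants", and for absent end-of-study values "we will use multiple imputation methods to impute missing 3-month values". The second analysis set is defined by completion: "The completer sample will comprise subjects who complete the 3-month follow-up".

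Three other places bear on the point:

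- Section 4.0 makes fasting plasma AGE and sRAGE primary endpoints, alongside feasibility and adherence.
- Section 10.0 schedules blood at Visit 1 and at Visit 2 (Week 14) only, so Visit 2 is the only source of a post-baseline value.
- Section 13.0 requires every adverse event to be characterized by "intensity/severity; expectedness; relatedness; frequency; outcome; treatment or action taken". It places monitoring at study visits and at the scheduled psychologist or dietitian contacts.

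**The concern.** The plan already separates adherence from participation in one situation: a woman who does not keep to her eating pattern remains in the study and is measured. It does not do so for a woman with a safety concern, who is placed with those who withdraw consent. She may be quite willing to give the remaining data.

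Two things are at stake. The first is the primary outcome, which would be missing for a reason connected with how the woman fared under her assignment, something an intent-to-treat analysis ought to capture where it can. The second is safety information: the women whose events matter most for judging tolerability are those for whom the plan sets out no follow-up after exit. The trial is a pilot meant to inform a larger trial on feasibility, adherence and variance, so both losses carry forward.

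**Working it through.** **1. Three situations after randomization, as Sections 10.0, 12.0, 13.0 and 14.0 treat them**

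| Situation | Stays in study | Post-baseline AGE/sRAGE | ITT value | Completer set | Stated route to adverse-event outcome |
|---|---|---|---|---|---|
| Stops or departs from the eating pattern | Yes | Measured at Visit 2 | Measured | Included | Scheduled contacts and Visit 2 |
| Withdraws consent | No | None if before Visit 2 | Imputed | Excluded | None stated |
| Removed for a safety concern | No | None if before Visit 2 | Imputed | Excluded | None stated |

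The second and third rows are identical, although only the second woman has declined further data collection. Sections 10.0, 13.0, 14.0 and 15.0 describe no status of being off the pattern but still followed, no early-exit blood draw and no contact after exit. The sensitivity check in Section 12.0 compares ITT, completer and imputation results. None of these uses a measured 3-month value from a woman in the third row, so the comparison cannot show whether such women differ.

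**2. The plan's own precision**

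Inputs: 22 per arm (Section 1.0), 10% attrition and 95% intervals (Section 12.0).

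- Evaluable per arm: 22 × 0.90 = 19.8, about 20.
- Within group: t(0.975, 19)/√20 = 0.468 SD. Stated: 0.47.
- Between groups: t(0.975, 38) × √(2/20) = 0.640 SD. Stated: 0.64.

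Both reproduce with 20 per arm. The printed 204 per arm would give 0.138 and 0.195, so it looks like a typing or text-extraction artefact and does not affect this point.

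**3. Possible shift in the TRF mean**

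The documents give no rate of safety exits. As a scale, 10% of 22 is 2.2, about 2 women, and 2/22 = 9.1% of the arm. Let k women leave for safety, and let their true values lie d SD from the values imputed for them (d = 0.5 to 1, an assumption). The shift is (k/22) × d:

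- k = 1: 0.023 to 0.045 SD
- k = 2: 0.045 to 0.091 SD
- k = 4: 0.091 to 0.182 SD

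**4. Precision**

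Measuring all 44 women would give a between-group half-width of 0.608 SD, against 0.640 SD at 20 per arm. Safety exits in the TRF arm beyond the planned 10% would widen it to 0.649 (19 vs 20), 0.659 (18 vs 20) or 0.670 (17 vs 20).

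**5. Contacts**

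Section 10.0 lists eight psychologist or dietitian contacts (Weeks 3, 4, 5, 6, 8, 10, 12 and 14). A woman leaving after Week 4 would have six of them, and Visit 2, still to come. That is close to the worst case, because Week 3 is the pre-intervention contact.

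**The case against.** The strongest reply is that much of this is silence rather than a stated rule. A reader might infer that any safety concern automatically ends all contact. The documents do not say so: no sentence states that contacts or Visit 2 stop, and the PI reviews each such event with the study team. That stands. What is explicit is the exception to remaining in the study and the treatment of ended participation as missing data. The loss of contacts and of Visit 2 follows only because nothing is provided afterwards.

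A reader might also infer that every woman who tolerates fasting poorly is lost. That is not supported. Sections 3.0 and 15.0 manage transient discomfort within the study, Section 10.0 allows eating outside the window on up to 2 days a week, and a woman who simply stops the pattern is non-adherent and retained. For the same reason it would be wrong to say that imputation draws only on women who tolerated TRF: measured values from non-adherent women are in the data, and the imputation model is not specified.

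Nor do the passages contradict one another outright. An all-randomized set with multiple imputation is coherent, and asking for the outcome of each adverse event implies some follow-up. The fault is a gap between them.

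That safety exits would fall mostly in the TRF arm is plausible, since Section 15.0 attributes headache, nausea, dizziness and fatigue to TRF. It remains a supposition: no rate is given, and the blood-draw and sensor risks apply to both arms.

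Finally, Visit 2 calls for a 12-hour fast, which is a real burden for a woman taken off a fasting regimen. The fix has to allow for that.

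**Conclusion.** The point holds for women removed from the study on safety grounds before Visit 2, and for them only. As written, their primary biomarkers are measured in neither analysis set, and the plan gives no route to the adverse-event outcome that it requires.

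The effect on the estimate is likely small: about 0.05 to 0.09 SD in the TRF mean, if 2 of 22 women are affected and an unmeasured difference of 0.5 to 1 SD is assumed, beside an interval of ±0.64 SD. The case rests less on numerical bias than on an avoidable loss of safety follow-up and on outcomes missing for a reason that may be linked to treatment. It should be corrected. It does not undermine the trial as a whole.

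**What to change.** Reconcile Sections 12.0, 13.0 and 14.0 so that stopping the eating assignment is a different event from leaving the study:

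- A woman whose assignment is stopped for safety and who still consents continues the contacts already scheduled and the Visit 2 outcome collection, wherever the investigator judges those procedures, including the 12-hour pre-visit fast, acceptable for her.
- Her measured values are used in the intent-to-treat analysis. Imputation is kept for values that could not be collected.
- The date and reason for stopping are recorded and reported by arm.

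When to stop the eating pattern, and whether any study procedure is safe for a given woman, remain the investigator's decision.

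The cost is a few sentences and a case-report field for the stop date and reason, which partly overlaps with the action-taken item already in the adverse-event record. The contacts and Visit 2 are already planned for every randomized woman. The downsides are that the intent-to-treat estimate may be slightly diluted by women who stopped TRF, and that Visit 2 places some burden on the women concerned.

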15.0 Risks to Subjects

Potential Risks.

Loss of confidentiality: Protection of patient confidentiality is essential in human subjects research. A HIPAA compliant de-identification process will be utilized which includes a unique computer-generated study ID for each enrolled patient. Study binders will be maintained in locked physical facilities and only accessible to authorized study team members to protect patient privacy. No data are stored when using Twilio; it only acts as a pass-thru. PHI is also not sent via text message; only the phone number is used to send the message including a unique link to their web accessible food survey submission.

Risks associated with blood collection include momentary discomfort and/or bruising, infection, excess bleeding, clotting, or fainting is possible, although unlikely.

CGM sensor risk may include mild pain associated with sensor insertion, infection, redness, bleeding and reaction to adhesive such as swelling, rash, itching.

Risks and or discomforts of time restricted feeding may include increased sensation of hunger, headache, nausea, dizziness, fatigue. These risks and or discomforts are transient, can be related to dehydration and can be minimized by avoiding dehydration. There may also be an adaption period to minimize these risks. Time restricted feeding is well tolerated with minimal side effects (17, 20, 31), from previous studies and PI ([name]) clinical experience.

In our study, subjects in both groups will have virtual visits with our psychologist or dietitian, through phone call or established doxy.me platform, at defined intervals throughout the study: pre-intervention, weekly for first month, alternate weeks for second month and once during last month of study. Our psychologist or dietitian will use data on patient self-report to enhance compliance with study group recommendations and address any patient concerns by use of motivational interviewing strategies. The study coordinator will make phone calls to subjects to encourage compliance. Such ongoing contact with psychologist or dietitian and research coordinator will help address any discomforts and enable use of behavioral strategies to address.

To allow for individual subject schedule and personal preference, we will allow patients in intervention group to self-select eating window of 8 hours to be completed by 8 PM.

We will use a fasting period of 16 hours in the intervention group. In a previous controlled study (20), daily fasting for 18 hours was reported as well tolerated and not difficult, but eating all meals within 6 hour period was reported as more difficult than the challenge of fasting for 18 hours per day. Participants reported eating within an 8 hour daily period would be feasible for most people. Based on these feasibility and acceptability results, we will use an eating period of 8 hours.

Overall, the risks involved in this study are truly minimal and therefore based on the potential personal benefit to the enrolled volunteers and the overall knowledge gained, reasonable.

16.0 Potential Benefits to Subjects or Others

Potential benefits to the study subjects.

Time restricted feeding has been previously shown to improve insulin resistance and inflammation. Interrupting AGE-RAGE signaling by TRF has potential for anti-inflammatory effect. Improvement in insulin resistance may lead to reduction in hemoglobin A1C and thus improvement in pre-diabetes. TRF has not previously been studied in relationship to AGE or sRAGE levels in the context of an experimental study of humans. Although our feasibility study is not powered to detect a statistically significant difference, we expect that the intervention group will demonstrate a clinically significant reduction in AGE and increase in sRAGE compared to the control group. Increases in sRAGE may represent a cancer risk modification by reducing AGE-RAGE toxicity, in this high-risk population.

It is possible that participating subjects in both groups will benefit from the regularly scheduled follow-up encounters with our psychologist or dietitian. This may afford them an opportunity to express concerns regarding their health and wellness, and may result in subsequent visits with appropriate health care providers.

Overall, the risks involved in this study are truly minimal and therefore based on the potential personal benefit to the enrolled volunteers and the overall knowledge gained, reasonable.

Potential benefits to science and society.

The results of this study are expected to directly impact studies of breast cancer risk modification by time restricted feeding. Our pilot study will obtain important feasibility information on process measures, including retention rate, virtual visits with psychologist or dietitian attended, adherence with food frequency questionnaires and overall adherence to eating pattern assigned (TRF vs control). This feasibility and adherence data will enable better future study designs and provide insight on ways to improve compliance.

Time restricted feeding has the potential to be a practical population wide cancer prevention strategy. Research findings will have limited or unknown external validity unless we answer complex implementation and dissemination questions. Telehealth has great potential during attempts to implement many new research findings. All the above has potential to mitigate cancer disparities through a practical, widely applicable and cost effective novel strategy.

Importance of the knowledge to be gained.

Results from our studies will identify the role of TRF in interrupting AGE-RAGE signaling, provide insight into adherence to TRF intervention: in women at high risk of breast cancer.

Results will provide the basis for larger intervention studies, investigating sRAGE as a novel modifiable cancer risk factor by TRF. The overarching broad long-term objective is to find a practical population wide cancer prevention strategy: Target AGE toxicity through TRF; to reduce breast cancer risk, incidence and recurrence.

17.0 Sharing of Results with Subjects

Prescreening results will be shared with subject at the time of prescreening. Individual subject lab results are shared upon subject's completion of study. Study results will be shared with subjects at the conclusion of study.

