Rationale for use of Freestyle Libre Pro Continuous Glucose Monitor (CGM): In post-menopausal women with pre-diabetes, we are studying the effect of time restricted eating on breast cancer risk biomarkers. One of our secondary outcomes is the effect of time restricted eating on measures of glycemia measured through CGM during baseline and end of study.

Rationale:

1. Metabolic syndrome which involves glucose dysregulation/hyperglycemia in pre-diabetes range is a marker for risk of breast cancer in post-menopausal women (1, 2).
2. Time restricted eating has been shown in studies of subjects with overweight and obesity to decrease fasting, mean and nocturnal glucose levels obtained through CGM. Other clinical trials have used Freestyle Libre Pro CGM in patients with metabolic syndrome (25), but not in the context of breast cancer risk biomarkers and not in a controlled trial, which our pilot study aims to do. Intervention studies in post-menopausal overweight women without diabetes but at high risk for breast cancer have used CGM to guide eating episodes and reported good compliance with CGM use and participants preference to wear CGM again (26).
3. Prolonged overnight fasting which our intervention: time restricted eating aims to achieve, has potential for reduction in breast cancer risk (4), but mechanisms remain uncertain.

One of the mechanisms may be improved glycemia from prolonged nighttime fasting (3). This requires study in randomized trials.

To study potential underlying mechanisms: In addition to advanced glycation end products as primary outcome, we aim to study glycemia as secondary outcome. Glycemia is best measured through continuous glucose monitoring rather than fasting glucose measured at Visit 1 and Visit 2, or self-monitoring of finger stick glucose by glucometer. The Freestyle Libre Pro CGM has been validated for 14 days of continuous use with factory calibration, will continuously record glucose for 2 weeks during baseline and end of study. Participants will be blinded to CGM data. CGMs estimate glucose with high accuracy and correlates with venous or capillary blood glucose. Use of CGM will avoid self-monitoring of glucose by finger stick 4-7 times per day which has been used by previous studies but is burdensome.

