Reason for video visit for freestyle libre insertion by patients during week 12 of study: We aim to limit participant burden and also limit costs of additional visit.

Participant will be trained during Visit 1 when first CGM is inserted, Video/phone visit for second CGM insertion will re-educate participants and help support insertion by participants.

The Freestyle Libre was designed to be inserted by medical providers or patients and has an easy use to applicator. We have experience with patients inserting the sensor. During the pandemic, other studies have used virtual visits to assist participants with CGM sensor insertion (29).

Visit 2, Week 14 (+/- 7days) Vital signs, weight, waist circumference, blood samples, 24 hour urine collection, questionnaires. The Freestyle Libre Pro CGM inserted by participants during week 12 will be removed during Visit 2.

Visits with psychologist or dietitian: through phone call or established doxy.me platform: pre-intervention, weekly for first month, alternate weeks for second month and once during last month of study, and at end of intervention.

Week 3 after randomization before start of intervention.

Week 4

Week 5

Week 6

Week 8

Week 10

Week 12

Week 14 before end of intervention.

The study coordinator may make phone calls and send text messages as needed to subjects to encourage compliance.

Visit 1 and Visit 2: Food Frequency Questionnaires (FFQ), sleep and exercise questionnaire.

Schedule of Events Table:

	Phone call	In-person or remote contact	Visit 1, Enrollment	End of Run in	Weeks 3,4,5,6,8, 10,12, 14	Visit 2 Week 14 (+/- 7 days)
Prescreening verbal consent, if indicated		X				
Inclusion/Exclusion	X					
Informed Consent		X				
Dispense urine collection supplies		X	X			
Fasting blood draw			X			X
24 hour urine collection			X			X
Text message all dietary intake			X	X	X	X
Placement of CGM sensor			X		Week 12 only	
Removal of CGM sensor				X		X
Vital signs			X			X
Questionnaires			X			X
Randomization				X		
Telemedicine or phone visit with psychologist or dietician				X	X	
Phone call by study coordinator to			As needed	throughout	the	study

encourage compliance						
----------------------	--	--	--	--	--	--

Protocol:

Prescreening point of care testing will be done at MUSC facilities or recruitment outreach events. Point of care testing will be done by the study team.

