SCTR Nexus clinic at MUSC will be used for study visits 1 and 2, to obtain vital signs, blood and urine collection. Subjects will be asked to avoid consumption of food, drink or caffeine, except water, for 12 hours prior to lab collection and avoid alcohol and exercise for 2 days before lab collection. Fasting blood samples (drawn after 12 hours of fasting in both groups to help match fasting duration), 24 hour urine collection, and food frequency (FFQ), power of food, food cravings, hunger and satiety, sleep and exercise questionnaires will be obtained before start of and at end of intervention. Subjects will be instructed to bring completed 24 hour urine collection to Visit 1 and Visit 2.

Patients will be provided remuneration for participation for each of the two visits and given food voucher after fasting lab draws.

Subjects in both groups will also fill out 2 week sleep diaries during 2 week run in period and last 2 weeks of intervention.

Subjects in both groups will have virtual visits with our psychologist or dietitian, through phone call or established doxy.me platform, at defined intervals throughout the study: pre-intervention, weekly for first month, alternate weeks for second month and once during last month of study. Our psychologist or dietitian will use data on patient self-report to enhance compliance with study group recommendations by use of motivational interviewing strategies. The study coordinator will make phone calls to subjects as needed to encourage compliance.

Blood and urine analysis: Plasma AGE and sRAGE (includes the cRAGE and esRAGE isoforms) will be measured by ELISA (as described in SA2). The Glasgow Prognostic Scoring System is a cumulative inflammation-based cancer-prognostic marker consisting of an assessment of serum elevation of CRP and decrease in albumin concentration by ELISA.

Samples for comprehensive metabolic panel, IGF-1, lipid panel, fasting insulin, uric acid, hemoglobin A1C, C-reactive protein and Apolipoprotein B will be obtained at baseline and at end of study (visit 1 and visit 2).

24-hour urinary AGE will be measured by fluorescence assay.

Urine creatinine will be assessed.

To assess renal handling and clearance, eGFR will be used to calculate AGE fractional excretion, and renal clearance of AGE will be calculated.

Dietary AGE analysis: Daily dietary AGE content from food frequency questionnaires will be estimated using methods we have published previously (30).

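### Section 17.0 holds individual lab results until a woman completes the study, with no stated exception for clinically important Visit 1 values

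*Combined protocol and SAP*

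**What the plan says.** Section 17.0 of the combined protocol and SAP sets three release points. Prescreening results are given at prescreening. For results obtained within the study, "Individual subject lab results are shared upon subject's completion of study". Overall study results follow when the trial ends.

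Section 10.0 lists the clinical tests: "Samples for comprehensive metabolic panel, IGF-1, lipid panel, fasting insulin, uric acid, hemoglobin A1C, C-reactive protein and Apolipoprotein B will be obtained at baseline", and again at the end of study. The first draw is at Visit 1, Week 0, before the run-in and before randomisation. The last is at "Visit 2, Week 14 (+/- 7days) Vital signs, weight, waist circumference, blood samples". Kidney function is needed for the renal analysis, since "eGFR will be used to calculate AGE fractional excretion". Section 2.0, in arguing for continuous glucose monitoring, refers to "fasting glucose measured at Visit 1 and Visit 2".

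Two provisions bear on safety. Section 13.0 says "Monitoring will be performed at each study visit by the study coordinator and PI, adverse events will also be monitored during regularly scheduled visits". Section 14.0 says that after randomisation "all will remain in the study unless consent is withdrawn or there are concerns regarding patient safety". That section also covers women who leave before randomisation: "Participants will be discontinued from the study after informed consent and run in period, if there is insufficient text message logging".

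**The concern.** Visit 1 can show something that nobody yet knows. Under section 5.0 the qualifying HbA1c or fasting glucose may be up to 12 months old at consent, and either one is enough. Section 10.0 offers a point-of-care HbA1c only to women with neither result in the last 12 months. Section 5.0 gives no time window for the lab review of AST, ALT or eGFR, so Visit 1 is the first liver and kidney measurement described within the study.

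Section 5.0 also shows which values the investigators think matter: AST or ALT at least 3 times the upper limit of normal, eGFR below 45, and a pre-diabetes range that ends at HbA1c 6.4% and fasting glucose 125 mg/dL. These are eligibility limits. I use them only as the plan's own markers of a value worth acting on.

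A woman with such a value at Visit 1 would, if section 17.0 is followed as written, hear of it when she completes. What she loses is time to clinical follow-up. The point is not that changing eating times would harm her, and it does not touch the trial's estimates.

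**Working it through.** **Inputs**
- Visit 1 blood draw: Week 0 (section 10.0).
- Run-in: 14 days (section 10.0).
- Randomised period: 12 weeks +/- 7 days (section 10.0).
- Release of individual results: completion of study (section 17.0), taken here as Visit 2.
- Enrolment ceiling: 60 (section 6.0).
- Laboratory turnaround: not in the documents; assumed at 0 to 14 days.
- The metabolic panel is assumed to report AST, ALT, creatinine (hence eGFR) and glucose.

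**Reproducing the plan's visit date.** 14 + 12 x 7 = 98 days, and 98 / 7 = 14.0 weeks. This agrees with the stated Week 14. The window gives 98 - 7 = 91 days (13.0 weeks) to 98 + 7 = 105 days (15.0 weeks).

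**Time a known result is held** = (days to Visit 2 - turnaround) / 7:

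| Assumed turnaround | Earliest Visit 2 | Latest Visit 2 |
|---|---|---|
| 0 days | 91 / 7 = 13.0 weeks | 105 / 7 = 15.0 weeks |
| 3 days | 88 / 7 = 12.6 weeks | 102 / 7 = 14.6 weeks |
| 7 days | 84 / 7 = 12.0 weeks | 98 / 7 = 14.0 weeks |
| 14 days | 77 / 7 = 11.0 weeks | 91 / 7 = 13.0 weeks |

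The 13 to 15 weeks run from draw to Visit 2. The time for which a known value is held is shorter by the turnaround. Notice on reporting would save the time in the table.

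**Same analyte, two rules.** A prescreening HbA1c is shared at once, and section 10.0 adds a handout and advice to follow up with primary care. A Visit 1 HbA1c waits for completion. The documents give no reason for the difference.

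**Whether other text closes the gap.** The monitoring in section 13.0 is built around adverse events. A baseline value drawn before any intervention does not naturally enter by that route. The team meetings in that section are quarterly, about 52 / 4 = 13 weeks apart, and cover progress, adverse events and data quality, so they would not reliably shorten the delay. Section 14.0 allows withdrawal for safety. None of these requires anyone to read the Visit 1 panel or to tell the woman.

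No probability or expected number of affected women can be worked out, because the documents give no rate of abnormal values.

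**The case against.** The case against has real weight.

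- **Unseen consent pages.** Return of individual results is often set out in the consent form, which is not in the file. An earlier-notice clause may exist there. This stands, so the fix is conditional.
- **Assay timing.** No section says when the clinical panel is run. Section 1.0 has plasma markers stored for later analysis, and section 11.0 describes transport to a research laboratory and freezer storage. If the panel is batched, no known value is being withheld. This stands too, and the delay is stated only for prompt assay.
- **A timetable is not a ban.** A reader might infer that section 17.0 forbids earlier contact. It does not. An investigator who saw a worrying value could act under the general safety commitments. What remains is that nothing requires it, and the one sentence on timing points the other way.
- **Early leavers.** A reader might take the 60 - 44 = 16 enrolled women who may not be randomised, plus about 0.10 x 44 = 4.4 lost at the planned attrition, as women left without results. The documents do not support that. Section 17.0 distinguishes the subject's completion from the conclusion of the study, and the natural reading is the end of each woman's own participation. The wording is unclear for leavers, but these figures do not measure harm.
- **Eligibility.** A reader might also infer that Visit 1 labs ought to be rechecked against section 5.0 before randomisation. Section 17.0 governs disclosure, not who is randomised. Section 5.0 accepts a qualifying HbA1c or glucose up to 12 months old, and a single Visit 1 HbA1c above 6.4% is not clearly a history of diabetes.
- **Holding results is defensible.** Participants are blinded to glucose-sensor data and are not asked to change diet or activity, so early disclosure could disturb behaviour. That is a sound reason to hold routine results, but a weak one for holding the few that need clinical follow-up.

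**Conclusion.** The concern holds in a limited form. As written, section 17.0 can leave a known, clinically important Visit 1 value undisclosed for about 13 to 15 weeks less turnaround: 12.6 to 14.6 weeks at an assumed 3 days, 11.0 to 13.0 weeks at 14 days. This rests on prompt assay, on completion meaning Visit 2 for a woman who stays in, and on the consent form not already providing earlier notice. The first and third cannot be checked from the documents, so confidence is moderate.

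It is a participant-safety and disclosure point. It does not bear on the endpoints, power or analysis. The change should be made because the gain to an affected woman is specific and the cost is small.

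**What to change.** Amend section 17.0 by adding an exception to the sentence on individual results:

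> *except that a study physician will review the Visit 1 comprehensive metabolic panel and HbA1c when they are reported, and AST or ALT at least 3 times the upper limit of normal, eGFR below 45, HbA1c above 6.4% or fasting glucose above 125 mg/dL will be disclosed promptly, with guidance to follow up with the primary care provider; women who leave early receive their results on leaving.*

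If the consent form already gives earlier notice, align section 17.0 with it instead. No change to the randomisation procedure is needed.

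The cost is physician review of at most 60 panels, on blood already drawn and with no added visit. If the clinical panel is now batched, it must be run in real time, which is a larger operational change. A few notified women may alter diet or activity, which could affect the glycaemic endpoints. If notice is given within the 14-day run-in it precedes randomisation and so does not depend on arm, which is a reason to aim for that window.
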